4.1 STUDY RATIONALE

This observational study has been planned to evaluate the effectiveness of Obinutuzumab in combination with chemotherapy in previously untreated advanced FL patients, in the real world setting in Italy.

The study will allow to collect real-life data in a significant number of Italian patients when compared to participants in pivotal studies of Gazyvaro and thus will allow to verify

in routine practice (after physician hands-on) the effectiveness and safety management in 50 reference sites all over the country.

The stratification factors selected to this study are different from those presented in pivotal trials as the label allows to treat patients in a wider setting than the clinical trials eligibility criteria. This stratification will also allow to understand the profile of patients that are treated with Obinutuzumab in Italy.

As described above, Obinutuzumab has granted approval for use in combination with chemotherapy, followed by Obinutuzumab maintenance therapy in patients with previously untreated advanced FL. Thus, the study will include patients with untreated advanced FL for which the physician has decided to use Obinutuzumab according to the approved SmPC. These patients will be treated according to the approved scheme, i.e. Obinutuzumab will be administered according to the approved SmPC in association with a chemotherapy regimen during induction, and alone during maintenance treatment.

Patients enrolled in this study may benefit from treatment with Obinutuzumab. However, the assignment of the patients to any therapeutic strategy and thus also to treatment with Obinutuzumab is not decided in advance based the study protocol and is clearly separated from the possibility or decision to include the patients in the study. Therefore, the treating physician will make all treatment decisions according to his/her regular practice independent of this study. During the study, patient will undergo clinical visits as planned by the treating physician, according to standard clinical practice.

Although Obinutuzumab has resulted to be generally well tolerated, IRRs have been reported with the use of the product, however occurring predominantly during infusion of the first 1,000 mg. These events will be closely monitored during the study and appropriate measures for prevention of IRRs (adequate glucocorticoid, oral analgesic/anti-histamine, omission of antihypertensive medicine in the morning of the first infusion, and the Cycle 1 Day 1 dose administered over 2 days) will be used in the study to reduce the incidence of IRRs, as scheduled in the current SmPC of the product. All AEs will be duly monitored in the study and appropriate measures (including the discontinuation of treatment with Obinutuzumab) will be implemented for the protection of patients' healthcare.

Therefore, treatment with Obinutuzumab offers the potential for clinical benefit in patients with untreated advanced FL for which the treating physician has decided to start treatment with Obinutuzumab.

Patients will be fully informed of the potential risks in taking part in this study, and investigators will make a careful assessment of the potential benefits and risks of Obinutuzumab, by monitoring the clinical status of the patient and the potential occurrence of AEs events and toxicities.

Therefore, the current evidence on the efficacy and safety of Obinutuzumab administered according to the therapeutic indication for the drug in patients with

untreated advanced FL suggest that the benefits that can be achieved from the participation in this observational study will outweigh the potential risks.

This trial will be conducted in compliance with the Declaration of Helsinki (1964 and amendments) current with the Good Pharmacoepidemiology Practice (GPP) published by the International Society of Pharmacoepidemiology (ISPE) and all other applicable laws and regulations.

For information on the condition under observation and on the Obinutuzumab please refer to the ~~Investigator's Brochure~~ and to the most recent version of the Summary of Product Characteristics (SmPC) of Gazyvaro®, i.e. the brand name of Obinutuzumab, for further details on nonclinical and clinical studies.

5. RESEARCH QUESTION AND OBJECTIVES

5.1 RESEARCH QUESTION

This study will evaluate the effectiveness and safety of Obinutuzumab in patients with previously untreated advanced follicular lymphoma (FL) treated with Obinutuzumab in routine clinical care.

5.2 OBJECTIVES

5.2.1 Effectiveness Objectives

The primary effectiveness objective of this study is as follows:

- To evaluate the effectiveness of Obinutuzumab in combination with chemotherapy in previously untreated advanced follicular lymphoma (FL) patients, in the real world setting as measured by the proportion of patients relapsed within 24 months from start of therapy (POD24).

The secondary effectiveness objectives of this study are as follows:

- To evaluate the progression free survival (PFS) at 2 and 3 years;
- To evaluate the overall and complete response rates at mid and end of induction, and during and after maintenance therapy (including the complete response rate at 30 months [CR30]), as per clinical practice, with and without 18F-fluorodeoxyglucose–positron emission tomography (FDG-PET);
- To describe patient/disease characteristics and the second line regimens prescribed for patients who progressed after first line therapy during the overall study duration and within 24 months from start of therapy (POD24);
- To explore the effectiveness of Obinutuzumab in different patient subgroups, stratified by follicular lymphoma International Prognostic Index (FLIPI) – intermediate and high, ECOG performance status (PS), age at study entry, chemotherapy backbone choice, hepatitis infection (history of past/resolved infection or latent HBV after prophylaxis as per standard treatment guidelines), presence of autoimmune disease, history of renal failure and liver failure.

5.2.2 Safety Objectives

The safety objectives of this study are as follows:

- To evaluate the safety of Obinutuzumab in a real-world setting.

5.2.3 Other Objectives

- To describe the treatment pattern in first and second line of treatment;
- To evaluate methods applied to tumour and response evaluations according to used guidelines and clinical practice;
- To evaluate the FDG-PET response at end of induction and end of maintenance, as per clinical practice;
- To evaluate the Quality of life;
- To evaluate the presence of B symptoms;
- *To explore effectiveness of Obinutuzumab in real world setting;*
- *To explore prescription profile*
- *To explore COVID-19 impact on therapy adherence*

6. RESEARCH METHODS

6.1 STUDY DESIGN

This is a retrospective and prospective primary data collection and secondary data use, non-interventional, multi-center study designed to assess real-world effectiveness and safety of Obinutuzumab in previously untreated advanced FL patients, prescribed in first line with Obinutuzumab and chemotherapy, according to existing label.

The study will be conducted in approximately 50 Italian centers distributed all across the country and will collect data during treatment with Obinutuzumab and up to 3.5 years following the start of the treatment. Since the study is observational, the treating physician will make all treatment decisions according to his/her regular practice independent of this study. No treatment regimen is mandated by this protocol.

Patients should be included after the start of treatment, including newly diagnosed FL patients. Patients included should have performed at least 2 cycles of induction treatment with Obinutuzumab and chemotherapy within 1 year from beginning of treatment.

During the treatment with Obinutuzumab, patient data will be collected at the clinical visits planned by the treating physician, including retrospective data of cycles performed before enrolment, baseline data and medical history, as detailed in Section 6.4.24. The collection of retrospective data will be those generated from the start of treatment with Obinutuzumab to study entry.

[figure not shown]
After cessation of Obinutuzumab treatment, patient data will be collected approximately every 3-6 months, as part of routine clinical practice visits, or remote contact, until loss to follow-up, withdrawal of consent or death, for up to 3.5 years following the start of Obinutuzumab treatment.

For each patient, the study will consist of a period of 42 months which can include: an induction treatment period (approximately 6 months) in which patients will receive Obinutuzumab and chemotherapy followed by a maintenance treatment period (approximately 24 months) in which patients will receive Obinutuzumab monotherapy and a follow-up period of one year, after the last Obinutuzumab administration. Patients will be followed for 3.5 years after the first treatment administration regardless of early discontinuation of treatment for any reason in any timepoint. Patients who discontinue treatment for reasons other than disease progression (e.g., toxicity, AE) will continue to have their data collected for tumor assessments performed as per clinical practice, until disease progression, withdrawal of consent, study termination by the Sponsor, or death, whichever occurs first, regardless of whether patients start a new anti-cancer therapy.

6.1.1 Overview of Study Design

A schedule of activities is provided in Appendix 2.

Figure 1 Study Scheme

Start Date of Study:

The study start date will be the date of the first data collection: the date from which information on the first study patient is recorded in the study database. The planned start date is July 2019.

End of Study:

The end of the study will be the date from which the last information of the last patient *still in the study* is recorded in the study database. The planned end date is December 2024.

The overall length of the study will be approximately 5 years.

This study will last 66 months. This period includes approximately 24 months of recruitment and 42 months after the last patient has started treatment with Obinutuzumab.

In addition, the Sponsor may decide to terminate the study at any time.

A data collection overview is provided in Appendix 2.

6.1.2 Rationale for Study Design

This will be an open-label, multicenter, national, non-interventional study. This was considered as the most appropriate design to evaluate the efficacy and safety of Obinutuzumab, administered during with chemotherapy during the induction phase and as monotherapy during the maintenance phase, according to the posology and method of administration approved in the current SmPc of Gazyvaro®, in patients with untreated advanced FL.

6.1.3 Number of Patients Observed in the Study

Approximately 300 patients will take part in this study.

6.1.4 Sites

This study will be conducted at approximately 50 sites in Italy.

Additional centers may be added or substituted if underperforming.

6.2 POPULATION

The patient population taking part in the study will comprise patients aged ≥ 18 years with untreated advanced FL.

Patients must meet the following criteria for study entry:

1. Signed Informed consent according to local regulations, after performing at least 2 cycles of induction treatment with Obinutuzumab and chemotherapy, within 1 year from beginning of treatment;
2. Age ≥ 18 years;

Patients who meet any of the following criteria will be excluded from study entry:

1. Any contraindications to Obinutuzumab therapy according to local label for specific indication;
2. Concomitant participation in an interventional clinical study;
3. Patients not receiving treatment for untreated follicular lymphoma with Obinutuzumab according to standard of care and in line with the current summary of product characteristics (SmPC)/local labeling

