6.4.2 Data Collected during the Observation Period

During therapy with Obinutuzumab, laboratory assessments are routinely performed in accordance with current guidelines and local standard of care. When performed during the observational period, available results that represent an adverse event in accordance to CTCAE vs. 5, relevant symptom/signal of an event or abnormal laboratory finding that results in a change of the treatment in study will be documented in the eCRF. Most data will be documented during the treatment period when the respective assessments are usually performed according to standard of care. The proposed assessments and suggested timings for assessments in the protocol/observational plan are not mandatory. It is up to the treating physician to perform and document the assessments as performed in the real clinical setting.

In the routine care setting, patients are seen regularly by their treating physicians either for treatment or for regular assessment after treatment. Thus, no study-specific visits or evaluations are required by this protocol.

Tumor assessments collected in eCRF will comprise the following periods as available:

- Baseline tumor assessment
- During induction:
 - Mid induction: tumor assessment performed between cycle 2 and cycle 4 after the start of treatments
 - End induction: tumor assessment performed at the day of cycle 6 /8 (or when induction is early discontinued) until 2 month later
- After induction treatment:
 - 1 year after the start of treatment (from 10 to 14 months after the start of treatment)

- 2 years after the start of treatment (from 22 to 26 months after the start of treatment)
- 3 years after the start of treatment (from 34 to 40 months after the start of treatment)
- 1 year after end of maintenance as applicable
- Any tumor assessment, and the method used that shows disease progression, CR or CRu during induction or maintenance.

The lack of tumor assessments in those periods are not a protocol deviation as clinical practice should be followed.

Since the enrolment of patients into the study will occur after the treatment has already started (Patients included should have performed at least 2 cycles of induction treatment with Obinutuzumab but no later than the completion of 1 year of the treatment with Obinutuzumab), a retrospective data collection is expected.

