7.2 INFORMED CONSENT

The sponsor's sample Informed Consent Form (and ancillary sample Informed Consent Forms such as a Child's Assent or Caregiver's Informed Consent Form, if applicable) *and the privacy form* will be provided to each site. If applicable, it will be provided in a certified translation of the local language. The sponsor must review and approve any proposed deviations from the sponsor's sample Informed Consent Forms or any alternate Consent Forms proposed by the site (collectively, the "Consent Forms") before IRB/EC submission. The final Consent Forms approved by the IRB/EC must be provided to the marketing authorization holder for archiving and for health authority submission purposes according to local requirements.

The Consent *and* Privacy Forms must be signed and dated by the patient or the patient's legally authorized representative before start of documentation of his or her data in the CRF. The case history or clinical records for each patient shall document the informed consent process and that written informed consent was obtained prior to first documentation of this patient's data in the CRF.

By signing the form, the patient confirms that he/she has been informed about the study and agrees to pseudonymous data collection, pooling of data with similar scientific data (if applicable), and the possibility of monitoring activities. It is the accountability of the physician *for ascertaining that the subject has comprehended the information and to obtain written informed consent from each patient participating in the study, after adequate explanation of the aims, methods, anticipated benefits, and potential hazards of the study. The physician must also explain that the patient is completely free to refuse to enter the study or to withdraw from it at any time, for any reason and without losing the benefit of any medical care to which the patient is entitled or is presently receiving.* A copy of each signed *and dated* Consent Form must be provided to the patient or the patient's legally authorized representative. All signed and dated Consent Forms must remain in each patient's study file or in the site file and must be available for verification by Site Operations Representative at any time.

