Data Collection (available data will be collected; no additional diagnostic or monitoring procedures will be applied to patients outside of routine clinical practice)	Enrolment visit ^a	Retrospective Data collection	Prospective Data Collected during Treatment Period (Induction and maintenance period)	Follow-up period ^b
Informed consent ^c	x			
Diagnosis confirmation (clinical stage, histology)		x		
Target Population	x	x		
Medical history and demographic data		x		
Concomitant treatments/medications ^d	x	x	x	
Treatment with Obinutuzumab	(x) ^e	(x) ^c	x	
Prophylaxis medication	x	x	x	
Laboratory assessments ^e	x	x	x	
Pregnancy test	x ^f	x ^f	x ^f	
Physical examination and Vital signs	x	x	x	
ECOG	x	x	x	x
B symptoms	x	x	x	x
QoL (Quality of life: EuroQol 5-Dimension Questionnaire, 5-level version (EQ-5D-5L); Functional Assessment of Chronic illness Therapy-Lymphoma (FACT-Lym) ^g	x		x	*
Chemotherapy regimen	x	x	x	
AEs/SAEs/AESI/SSIRR/ADR	x		x	x ^k
Retrospective Safety data collection		x ^h		
Tumor assessments	x	x	x	x
Ann Arbor	x	x		
FLIPI score assessment ⁱ	x	x		
BM evaluation	x	x	x	x
Response rate ^j	x	x	x	x
New anti-cancer therapy and survival status after end of treatment				x

^a Items Concomitant treatments/medications, Treatment with obinutuzumab, Pregnancy test. Physical examination and Vital signs, Prophylaxis medication and Chemotherapy regimen apply only for patients still on treatment at the time of enrollment as part of their standard procedures for treatment. In case of patients

enrolled after treatment completion, these data will be collected as indicated in the Retrospective column and the prospective information will be collected as described in the Follow-up period.

^b Approximately one-year follow-up after last dose of Obinutuzumab administration, as per clinical practice, or for patients that early discontinue the treatment up to 3.5 years after first treatment administration or until withdrawal of consent, study termination by the Sponsor, or death, whichever occurs first, regardless of whether patients start a new anti-cancer therapy. For patients that discontinue treatment before completing induction or maintenance, the follow up parameters can be collected in accordance with current patient's schedule visit and not every 2 months. Follow-up data will include at least tumor assessments, *new anti-lymphoma therapy informations*, and safety data.

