2.4 SECONDARY OUTCOME MEASURES

2.4.1 Secondary Effectiveness Outcome Measures

- Progression free survival (PFS) at 2 and 3 years, defined as the time from the date of treatment initiation until the first documented progression of disease measured by routine clinical care or death from any cause, whichever occurs first. Patients who have no disease progression and have not died or who are lost to follow-up at the time of analysis will be censored at the date of last tumor assessment where no progression was documented or the last date of follow-up for disease, whichever is last. Patients without post-baseline tumor assessments will be censored at the time of their baseline visit unless death occurs prior to their first scheduled tumor assessment;
- Time to next treatment (TTNT), defined as the Time to initiation of subsequent systemic anti-cancer therapy following initiation of Obinutuzumab containing therapy. Patients not starting a subsequent systemic anti-cancer therapy will be censored at the date of the last study visit;
- Overall survival (OS), defined as the time from initiation of study treatment to death from any cause. Patients who still alive at the time of analysis and patients who are lost to follow-up will be censored at their last time known to be alive;
- Correlation between POD24 and OS;
- TTLCB, defined as the time from first dose to loss of clinical benefit as assessed by the treating physician (single or multiple reasons possible: e.g. disease progression, deterioration in ECOG PS, death, other). Patients who do not loss clinical benefit will be censored at the date of the last study visit. Patients without post-baseline tumor assessments will be censored at the time of their baseline visit unless death occurs prior to their first scheduled tumor assessment;
- Overall response rate (ORR);
- Complete response (CR);
- Complete response at 30 months (CR30);

- Duration of response (DoR) measured per clinical practice, defined as the time from first documentation of CR or partial response (PR) (whichever occurs first) until disease progression, as evaluated by the physician according to routine clinical practice or death. Patients who have no disease progression and have not died or who are lost to follow-up at the time of analysis will be censored at the date of last tumor assessment where no progression was documented or the last date of follow-up for disease, whichever is last;

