3.1 ANALYSIS POPULATIONS

The following populations will be considered for data analysis:

Effectiveness population

Effectiveness analysis population includes all patients who are enrolled and have received at least two cycles of Obinutuzumab.

Safety population

Safety analysis population includes all patients who are enrolled.

Screening failures are not considered for the analyses.

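### OS and PFS are timed from first dose, but patients enter only if alive to consent after two cycles and up to a year later; without delayed entry both look somewhat too good

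*Protocol*

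**What the plan says.** **Entry.** Protocol 6.2 requires consent "after performing at least 2 cycles of induction treatment with Obinutuzumab and chemotherapy, within 1 year from beginning of treatment". Protocol 6.4.2 repeats the upper limit: "no later than the completion of 1 year of the treatment with Obinutuzumab". Protocol 7.2 requires the consent form to be signed "before start of documentation of his or her data in the CRF".

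**Time origin.** SAP 2.4.1 has "Overall survival (OS), defined as the time from initiation of study treatment to death from any cause". PFS (same section) and POD24 (SAP 2.3) also start at treatment initiation, as in protocol 6.3.1 and 6.3.2. Protocol 6.7.1 and SAP 3.2, however, state as a general rule that both event and censoring times are counted from the enrolment date.

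**Handling.** Neither document mentions delayed entry, left truncation or a landmark. Protocol 6.7.1 promises further work on several kinds of bias. SAP 3.4 plans no sensitivity analysis. Protocol 6.9 and SAP 3.7 acknowledge selection bias only in general terms.

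**Safety set.** SAP 3.1: "Safety analysis population includes all patients who are enrolled". Since enrolment already requires two cycles, this is in effect the same set as the effectiveness population. Protocol 4.1 describes infusion reactions as "occurring predominantly during infusion of the first 1,000 mg".

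**The concern.** The interval from first dose to consent is one that a patient must survive in order to be counted. Deaths in that interval are missing by construction. If OS is then read from first dose with everyone at risk from time zero, the denominator includes months in which no enrolled patient could have died. This is left truncation. It favours the drug, and a larger sample does not reduce it. OS is hit directly. PFS is affected because patients who die before consent, with or without progression, are absent. The same entry rule removes from the safety set anyone who stopped before completing two cycles, so rates of adverse events, infusion reactions and discontinuation do not describe all patients who start the drug.

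**Working it through.** **1. The plan's own figure.** Protocol 6.7.5 gives a 95% Clopper-Pearson width of 7.9 points for POD24 of 13% with n = 300. With 39/300 the interval is 9.41% to 17.34%, width 7.93. It reproduces, and the stated half-width of 3.95 points is the yardstick below.

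**2. Assumptions.** The latest entry, 12 months, is from protocol 6.2. The earliest, about 1.5 months, is my reading of two cycles in an induction of about 6 months. The documents do not give the lag distribution or mortality. I take the lag as uniform from 1.5 to *L* months, with *L* = 6 or 12, and annual mortality *m* of 2–4% at constant hazard *h* = −ln(1−*m*)/12 per month.

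**3. OS, closed form.** The share of starters still alive at consent is *W* = [exp(−1.5*h*) − exp(−*Lh*)] / [*h*(*L*−1.5)]. The uncorrected 3-year OS among the enrolled is exp(−36*h*)/*W*. For *m* = 3%, *h* = 0.002538. With *L* = 12, *W* = 0.98304 and 91.27/0.98304 = 92.84%. With *L* = 6, *W* = 0.99053 and the result is 92.14%.

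| Annual mortality | True 3-year OS | Read, lag 1.5–6 | Read, lag 1.5–12 |
|---|---|---|---|
| 2% | 94.12 | 94.72 (+0.60) | 95.19 (+1.07) |
| 3% | 91.27 | 92.14 (+0.87) | 92.84 (+1.57) |
| 4% | 88.47 | 89.61 (+1.14) | 90.52 (+2.05) |

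At 3% mortality and the longer lag, first-year mortality is read as 1.33% instead of 3.0%, which is 44% of it.

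**4. All three endpoints, selection on being alive only.** This is a simulated illness-death model: progression hazard set to 13% at 24 months, 1–3% annual death without progression, median survival after progression 12–24 months, lag 1.5–12. 3-year OS rises by 0.9–2.0 points and 3-year PFS by 0.8–1.8. POD24 falls by 0.4–0.7. Repeating it with lag 1.5–6, the POD24 fall is 0.1–0.2.

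**5. Upper bound for POD24.** Suppose no patient who progressed before consent is enrolled. With *h* = −ln(0.87)/24 = 0.005803 and lag 1.5–12, *W* = 0.9617, and POD24 reads 1 − 0.87/0.9617 = 9.54%, about 3.5 points low.

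**6. Does delayed entry work?** From the model in step 4, 3-year figures in %:

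| Death without progression per year; median survival after progression | OS: all starters / uncorrected / delayed entry | PFS: all starters / uncorrected / delayed entry |
|---|---|---|
| 1%; 24 months | 90.07 / 90.97 / 90.23 | 78.72 / 79.51 / 79.60 |
| 3%; 12 months | 81.34 / 83.33 / 81.60 | 74.15 / 75.96 / 75.02 |

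For OS nearly all the bias goes. For PFS the gain is smaller, because the delayed-entry curve is conditional on being event-free at about 1.5 months and drops progressions recorded before consent.

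**7. Cost in precision (OS).** With delayed entry the relative variance is roughly proportional to ∫dt/p(t), where p(t) is the share already enrolled at month t. Starting the curve at month 3:
- lag 1.5–12: 10.5·ln(10.5/1.5) + 24 = 44.4, against 36 − 6.75 = 29.25 for the uncorrected estimate; √(44.4/29.25) = 1.23;
- lag 1.5–6: 4.5·ln(4.5/1.5) + 30 = 34.9, against 36 − 3.75 = 32.25; √(34.9/32.25) = 1.04.

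So intervals widen by about 4–23%. Simulation with n = 300 gave 4% and 21%. Starting instead at 1.5 months, where hardly anyone is at risk, gave about 30–80%.

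**8. Delayed entry applied to POD24.** By step 5, the share of POD24 events falling before consent is (1 − 0.9617)/0.13 = 29% with the longer lag. With the shorter lag it is about 0.0215/0.13 = 17%. These are recorded events that would be thrown away.

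**The case against.** **The clock may start at enrolment.** Under protocol 6.7.1 and SAP 3.2, survivors would not be credited with the interval before consent. That is true, but it does not rescue the plan. It contradicts every endpoint definition and the primary objective, which counts 24 months from the start of therapy. Progressions before consent would get negative times. A 24-month window could reach 36 months from first dose. A patient consenting at month 12 would have only 42 − 12 = 30 months of follow-up, too short for any 3-year figure.

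**A reader might infer that early progressors are also selected out, so that POD24 is biased by some 3.5 points.** The documents do not support that. Progression before consent is not an exclusion. Retrospective tumour assessments are collected (protocol 6.4.2), so a living patient who progressed at month 5 can enrol and counts as a POD24 event. Exclusion 2, "Concomitant participation in an interventional clinical study", bars only current participants in such a study. Exclusion 3 reads most naturally as an on-label condition. Appendix 2 note a provides for patients "enrolled after treatment completion, these data will be collected as indicated in the Retrospective column". Deaths unrelated to progression within 24 months leave the POD24 analysis anyway. What remains is that the number of progressors not approached is unknown and no table would show it.

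**The safety gap has no number.** This is correct. First-infusion reactions of enrolled patients are collected retrospectively, and the documents do not say how many patients stop before two cycles. The point is one of labelling.

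**The study is single-arm, tests no hypothesis and discloses selection bias.** This lowers the stakes, but the general disclosure does not name this mechanism, which can be corrected for OS.

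**Conclusion.** The point holds for OS and, to a lesser degree, PFS: deaths before consent are structurally missing and the plan does nothing about it. The overstatement of 3-year OS is roughly 0.6–2 points. It rests on an assumed 2–4% annual mortality, constant hazards, and a consent lag spread evenly over 1.5–6 or 1.5–12 months. For POD24 the structural bias of about 0.4–0.7 points (longer lag) is well inside the planned 3.95-point half-width. The 3.5-point figure is an upper bound that needs every living patient who progressed before consent to go unenrolled, which the criteria do not require. The two time origins must be reconciled in any case. This should be fixed before the final analysis, but it does not undermine the primary endpoint.

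**What to change.** **SAP 3.2**
- Make first dose the single time origin and delete the enrolment-origin rule, with the matching correction in protocol 6.7.1.
- Estimate OS on that scale with the consent date as entry time. Fix in advance the month at which the curve starts, with a minimum number at risk, and label the result as conditional on being alive then.
- Report PFS with delayed entry as a sensitivity analysis beside the planned estimate, and amend SAP 3.4 accordingly.
- Keep POD24 as planned, counting recorded progressions before consent. Show how many POD24 events preceded consent, and tabulate time from first dose to consent.

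**SAP 3.1 and 3.3**
- State that adverse event, infusion reaction and discontinuation rates apply to patients who completed at least two cycles, not to all who start the drug.

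**Cost.** The consent date is already needed for enrolment, so this is SAP wording and one extra argument in the R survival call. OS intervals widen by about 4–23% if the curve starts at month 3, and by much more if it starts at 1.5 months. Early risk sets are small: at month 3, about 300 × 1.5/10.5 = 43 patients with the longer lag, or 300 × 1.5/4.5 = 100 with the shorter. Nothing can be learned about roughly the first 1.5 months, and the method assumes that the timing of consent is unrelated to prognosis.

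**Not needed.** Delayed entry for POD24 would discard 17–29% of recorded events to correct a small bias. Rewording eligibility would need an amendment and ethics approval (protocol section 3), and planned recruitment (July 2019 plus about 24 months) had ended before the SAP was signed in February 2022.
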